6. STATISTICAL METHODS

6.1.1.1. DATA QUALITY ASSURANCE

All tables, figures and data listings to be included in the report will be independently checked for consistency, integrity and in accordance with standard Menarini Ricerche procedures.

6.1.1.2. GENERAL PRESENTATION CONSIDERATIONS

This section describes the statistical analyses, presentation of the results, and the study endpoints/measures that will be collected and/or derived during the study at the time points specified in the Schedule of Events.

General Considerations

The software used for all summary statistics and statistical analyses will be SAS® 9.1.3 or higher (SAS Institute, Inc.).

Standard descriptive statistics

Unless specified otherwise, the following standard descriptive statistics will be presented, by treatment group and overall, for continuous and categorical variables:

Continuous variables

Number of non-missing observations, mean, standard deviation, standard error of the mean, median, minimum, maximum. Specific descriptive statistics may be performed for the PK analyses.

Categorical variables

Number of non-missing observations and percentage (%), defined as the number of non-missing observations in the considered treatment group divided by the number of non-missing observations overall in the considered cohort. If the count is 0 for a category, the percentage will not be displayed.

Descriptive summaries will be presented with the same precision (number of decimals) as the original data for the minimum and the maximum. Mean and medians will be presented to 1 decimal place greater than the original data. Standard deviations and standard errors will be presented to 2 decimal places greater than the original data. Ratios will be rounded to 3 decimal. Percentages will be presented to 1 decimal place.

Definition of baseline

The baseline record will be defined as the last available (non-missing) value before or on the date of first administration (Visit 1) for Cycle 1.

Patient Disposition and baseline tables

Patient Disposition

The number of patients screened, the number of patients screen failed, and the number of patients in each population (DLT, safety, efficacy, PP, PK) will be presented by cohort. For this table, the percentages will be calculated using the total number of patients dosed in the cohort as the denominator when appropriate

The number and percentage of patients who discontinued and reasons for discontinuation will be summarized by cohort. All data relating to study completion or discontinuation and inclusion in the analysis populations will also be listed.

Demographic data

Demographic and baseline characteristics, including age, gender, race will be summarized by cohort. All demographic data recorded on the eCRF will be listed.

Medical History and Concurrent Medical Conditions

Medical history will be coded using the Medical Dictionary for Regulatory Activities (MedDRA version 15.1). The number of patients with at least one recorded medical history or current medical condition will be presented using frequency counts and percentages as well as an incidence table by System Organ Class (SOC) and Preferred Term (PT). The safety population will be used for this summary. Details of medical history will be provided in listings.

Safety Analyses

Safety evaluations will be performed using the safety population.

Adverse Events

AEs will be categorized as Treatment-Emergent Signs and Symptoms (TESS) or Non-TESS for each of the study periods defined below. If an AE occurs for the first time or if it worsens in terms of seriousness or severity after the first study drug intake, it will be classified as TESS, otherwise it will be classified as non-TESS. Each adverse event will be classified according to the grade (Grade 1 to 6) depending on severity of the event, as specified in Section 8.6.1.5 of the Study Protocol.

The following periods are defined for assignment of TESS:

- Cycle 1: date of the administration to the day before the administration of Cycle 2 or, if the subject is discontinued, until the end of study.
- Cycle n: date of the administration to the day before start of Cycle n+1.

The following rule will be applied for each period: Period start date \leq AE start date \leq Period stop date.

The maximum relationship to study drug will be reported for the respective summaries. All AEs summaries will be based on the Safety population.

In particular grade ≥ 2 ADR will be listed since the occurrence of grade ≥ 2 ADR is associated with the switch from an ATD design to a 3+3 design.

The intensity of an adverse event is reported on the eCRF using the following definitions:

- **Mild:** It does not interfere with routine activities;
- **Moderate:** It interferes with routine activities;
- **Severe:** It makes it impossible to perform routine activities.

The maximum intensity will be used for the summaries; all events will be included in the listings.

Missing intensity will be left as missing and categorised as such.

Serious Adverse Events (SAEs) are defined in Section 8.6.3 of the Study Protocol

A Treatment-Emergent SAE is defined as a TESS event classified as serious.

An AE will be classified as related to study drug if causality was recorded as “certainly related”, “probably related”, “possibly related”, “unassessable/unclassifiable”. Missing causality will be considered as related.

An overview of TESS will be provided with the number and percentage of patients reporting an event by cohort and overall for each period. The summaries will be presented for the following categories:

- Any TESS

- Any TESS by grade (<2, >=2)
- Any Serious TESS
- Any mild/moderate/severe TESS
- Any TESS leading to study drug discontinuation
- Any TESS leading to temporary study drug administration interruption
- Any related TESS (by categories)

If a patient has more than one occurrence of a TESS, the patient will be counted only once within that preferred term. The same applies to serious TESSs and drug-related TESSs.

Additionally, the following summaries of TESSs expressed as number and percentage of patients with TESSs will be presented by SOC and PT by cohort and overall, for each period:

- TESS
- Serious TESS
- Serious TESS resulting in death
- TESS of Grade >=2
- TESS of Grade <2
- TESS by intensity (by categories)
- TESS leading to study drug discontinuation
- Serious TESS leading to study drug discontinuation

Drug-related TESSs will be summarized in the same way that TESS as it is described above.

Moreover, the following summary will be presented for drug-related TESS:

- Number of events, number of patients and percentage of patients with DLT by SOC and PT

In the final TFL a summary of TESSs by period and Grade will be reported.

All adverse events (including non-TESS or AEs happening after End of Study Visit of the patient) recorded on the eCRF will be listed. A separate list of serious adverse events will be provided. TESS will be flagged in the listings.

Laboratory data

All laboratory data will be listed.

Clinical chemistry, haematology and urinalysis parameters will be summarized by parameter, visit and cohort using descriptive statistics. The change from baseline will be summarized for each post baseline visit with descriptive statistics by cohort and visit.

Summary statistics will also include the number and percentage of patients with Normal, Abnormal NCS (Non Clinically Significant) or Abnormal CS (Clinically significant), by parameter and visit. Shift tables will be presented with the counts of individual shifts from each of the reference range categories from baseline to post-dose by laboratory parameter, cohort and visit.

All laboratory data will also be reported in listings.

Previous/ Concomitant medication

All medication taken within 30 days before enrolment and taken during the study will be listed. Medication will be coded using the WHO drug dictionary (version C_DD_Jun2012-WithPrefTerm) and summarised by PT and by anatomical therapeutic chemical (ATC) category level X.

Previous medications are those which start within 30 days prior to enrolment and stopped prior to first dose of study drug. Concomitant medications are those which are started on or after date of first induction, or started prior to induction and stopped after or are ongoing.

The number and percentage of patients of previous and concomitant medication will be tabulated and summarized for concomitant medications.

Any previous and concomitant medication record will also be presented in a listing.

Electrocardiogram (ECG) Evaluations

ECG judgment collected on the eCRF will be summarised descriptively by cohort and visit. Similarly, changes from baseline for each post baseline visit will be summarised.

Vital Signs Evaluations, weight

Vital signs (systolic and diastolic BP (Blood Pressure - mmHg), weight reported in kilograms (kg), heart rate), will be summarised descriptively by cohort and visit. Similarly, changes from baseline will be summarised for all scheduled post baseline visits.

All vital signs parameters will be listed.

Physical Examinations

Physical examination findings (Normal, Abnormal NCS or Abnormal CS) will be summarised using descriptive statistics by Body System, cohort and visit.

Abnormal NCS or Abnormal CS findings on physical examination will be presented in a listing.

Efficacy Analyses

During CRC meeting no efficacy data can be analyzed since efficacy assessment (MRI TC PET scan) will be repeated every 2 cycle.

The efficacy will be evaluated at the end of the study.

Pharmacokinetics Analysis

Pharmacokinetics section will be present upon availability of laboratory data.

Plasma concentrations will be reported for each time point.

PK parameters will be reported with:

number of non missing observations (N), mean, standard deviation (SD), geometric mean and its 95% confidence interval (CI), minimum, median, maximum and coefficient of variation (CV %).

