9.3 STATISTICAL ANALYSIS

9.3.1 Descriptive statistics

All study variables will be presented by dose-cohort and overall, using the appropriate descriptive statistics according to the variable nature, unless otherwise specified:

- Continuous variables: number of non-missing observations, arithmetic mean, standard deviation (StDev), standard error (SE; for PK variables), minimum, median, maximum (and geometric mean and its 90% confidence interval [CI] for PK variables).
- Categorical variables: number of non-missing observations and column percentages (N, %).

- Time to event variables: number of non-missing observations, number and percentage of censored observations, 1st quartile, median (and its 95% CI), 3rd quartile, Kaplan-Meier survival curves and event rate every two cycles, and at the End of Study Visit and at the End of Study, as appropriate.

The behavior over time of study variables will be summarized by treatment cohort and overall as follows:

- Continuous variables: descriptive statistics for each time point and for the absolute/percentage differences to baseline. For PK variables, only descriptive statistics for each time point will be used.
- Discrete variables: descriptive statistics for each time point and shift tables to baseline.

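### The SAP's default definition of a categorical percentage omits the category count; it is the SAP's only rule for response rates and baseline categories, and by-cycle AE tables have no at-risk denominator

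*SAP*

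**What the plan says.** SAP 6.1.1.2 introduces its standard statistics as a default: "Unless specified otherwise, the following standard descriptive statistics will be presented, by treatment group and overall, for continuous and categorical variables". For categorical variables it then asks for a count and a percentage, the latter "defined as the number of non-missing observations in the considered treatment group divided by the number of non-missing observations overall in the considered cohort". The next sentence adds: "If the count is 0 for a category, the percentage will not be displayed".

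Protocol 9.3.1, repeated in the synopsis, has a different rule. Its bullet opens "Categorical variables: number of non-missing observations and column percentages (N" and the bracket goes on to the percent sign.

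Some SAP tables carry more specific wording, all within 6.1.1.2:

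- **Disposition:** "the percentages will be calculated using the total number of patients dosed in the cohort as the denominator when appropriate".
- **Adverse events:** "An overview of TESS will be provided with the number and percentage of patients reporting an event by cohort and overall for each period". Each cycle is a period, and all AE summaries use the Safety population.
- **DLT:** "Number of events, number of patients and percentage of patients with DLT by SOC and PT", listed among the drug-related AE summaries.
- **Laboratory:** number and percentage of patients who are normal, abnormal not clinically significant, or abnormal clinically significant, by parameter and visit.

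For efficacy, SAP 5.1.1.2 names response rate and disease control rate (Step 1) and complete and partial response (Step 2). It gives no formula, and the efficacy paragraph of 6.1.1.2 says only that efficacy will be evaluated when the study ends. Gender and race are to be summarised by cohort with no further rule.

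**The concern.** A percentage for a category needs the number of patients in that category as its numerator. The SAP formula has a non-missing count above the line and another below it, so it cannot return the proportion of patients with any characteristic. The SAP also does not say how a treatment group differs from a cohort in this single-arm study, so even the literal ratio is ambiguous.

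Protocol 9.3.3 and 9.3.4 analyse efficacy and safety by descriptive statistics only, so these percentages are much of what the trial will report. Where no specific wording replaces the default, the programmer must either follow a rule that gives a wrong number or depart from the SAP. Where the wording names a numerator but no denominator, as in the by-cycle AE tables, the choice is left open in an open-label study.

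**Working it through.** The documents report no percentage calculated with this formula, so there is no planned figure to reproduce. The check applies the formula to the one cohort whose counts are given.

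**Inputs**

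- 1.60 mg/kg cohort: 6 patients treated and followed through the DLT window (Protocol 6.2.3).
- DLTs: 1 (Protocol 6.2.3; 6.3, item 3).
- Planned patients: 100 in Step 1 and 22 in Step 2, 122 in all (SAP 6.1.1.4).

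**Literal formula, treatment group = dose cohort**

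Non-missing in group / non-missing in cohort = 6/6 = 100%. The event count does not enter, so the result is 100% for any count from 0 to 6.

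**Literal formula, denominator = a larger set**

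The SAP does not define the larger set, so these totals are assumptions:

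| Assumed total | Ratio |
|---|---|
| 11 (five single-patient cohorts below 1.60 mg/kg, plus 6) | 6/11 = 54.5% |
| 100 (planned Step 1) | 6/100 = 6.0% |
| 122 (planned total) | 6/122 = 4.9% |

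Each is the cohort's share of the patients, not an event rate.

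**Category count over non-missing count in the same column**

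1/6 = 16.7%. This is the natural meaning of a column percentage.

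The DLT counts are used because they are available. They show what the formula does, not what the DLT table would print, since that table names its own numerator.

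**Where the default is the SAP's only rule**

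| Table | Numerator stated elsewhere in SAP | Denominator stated elsewhere in SAP |
|---|---|---|
| Disposition | yes | yes, patients dosed in the cohort |
| AE by cycle | yes | Safety population; nothing on patients reaching the cycle |
| DLT | yes | by placement, Safety population, although a DLT population is defined |
| Laboratory by visit | yes | no |
| Response, disease control | no | no |
| Gender, race | no | no |

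**Size of the denominator gaps (assumed counts)**

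- By cycle: 8 patients with an event among 20 dosed in a late cycle, from a set of 40, give 8/20 = 40% or 8/40 = 20%.
- DLT: if one further patient were dosed but not evaluable and was replaced, 1/6 = 16.7% on the DLT population becomes 1/7 = 14.3% on the Safety population.
- Response: SAP 8.1.1.2 makes an ITT population the default for tables, but it is not among the five populations in SAP 6.1.1.3. The response denominator is therefore not fixed there either.

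**The case against.** The strongest reply is that this is a drafting slip with little reach. The rule about a zero count for a category makes sense only if the category count is the intended numerator. The formula yields to more specific text. The protocol already prescribes column percentages, and the SAP describes itself as giving further detail on the protocol's methods. Adverse events and laboratory data are also listed in full, so proportions can be recomputed. All of this stands, and it limits the point to a correction of wording and denominators.

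A reader might infer more than the documents support:

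- **That every percentage in the report is wrong.** The formula is a default, and disposition has its own denominator.
- **That the AE, DLT and laboratory tables would show 100%.** Their wording asks for the percentage of patients with the event or in the category, which supplies the numerator. What the by-cycle AE tables lack is the denominator.
- **That the MTD is affected.** It rests on a count, no more than 1 of 6 patients with a DLT (SAP 5.1.1.1), with committee review of each escalation.
- **That correcting the formula breaks pre-specification.** Column percentages are the protocol's own rule, so the correction restores it.

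The reply does not supply a SAP formula for response and disease control rates, or a denominator for a cycle that only some patients reach. The protocol's column percentages would still apply to the response rates, but they do not say which population forms the column.

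**Conclusion.** The default definition is wrong as written and conflicts with the protocol. Followed literally for six patients with one event, it gives 100%, or the cohort's share of a larger total (4.9% to 54.5% for the totals assumed), in place of 16.7%. In practice the error bears on response rate, disease control rate, complete and partial response in Step 2, and baseline categories, where the SAP offers nothing else. The missing by-cycle denominator is a related gap and could halve a late-cycle AE percentage under the assumed counts.

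The correction is small. The dose-escalation decisions and the MTD do not depend on it.

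Two assumptions apply. Treatment group is taken to mean dose cohort, the natural reading in a single-arm study. The list of tables in SAP 8.1.1.3 has a heading but no content in the text available, so table-level denominators set out there could not be checked.

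**What to change.** Replace the percentage sentence in SAP 6.1.1.2 with:

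> n (%) = number of patients in the category divided by the number of patients with non-missing data in the same column (dose cohort or overall) of the stated analysis population. For AE tables by cycle, the denominator is the number of Safety-population patients dosed in that cycle. For by-visit tables, it is the number of patients with a non-missing assessment at that visit. The number missing is reported but not included in the denominator.

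Then name the DLT population for DLT percentages and the Efficacy population for response and disease control rates.

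The non-missing denominator keeps to Protocol 9.3.1 and the observed-cases approach of Protocol 9.3.5. Dividing by all patients with missing as a category would depart from both.

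The cost is a few sentences in the SAP, with no new data and no protocol amendment. They should be in place when the SAP is finalised, which Protocol 9.5 requires before database lock.

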NOTE: safety laboratory tests performed within 24 hours prior to Day 1 are accepted and do not need to be repeated at Visit 1 (Day 1) prior to study drug administration.

- Dose Cohort assignment
- PK blood sampling (pre-infusion)
- Tumor Lysis Syndrome (TLS) risk assessment according to Investigator's TLS manual (see Appendix II)
- TLS prophylaxis if applicable (see Appendix II)
- Premedication
- Recording of AEs and change in concomitant medication

Study drug administration

- Study drug administration, given as a 3-hour IV infusion
- Vital signs every 15 minutes during the first hour of study drug administration and then at every hour until the end of infusion. In case of temporary infusion interruption, vital signs should continue to be collected every 15 minutes until the first hour post-infusion re-start and then every hour until the end of infusion (or until 1-hour after the permanent infusion interruption)
- Continuous ECG monitoring during the IV infusion up to 30 minutes after the end of infusion and 12-lead ECG record 30 minutes after the end of infusion
NOTE: If ECG monitoring equipment is not available, heart rate should be monitored up to 30 minutes after the end of infusion and 12-lead ECG recorded at 30, 60 and 120 minutes during the IV infusion with final 12-lead ECG record at 30 minutes after the end of infusion.
- PK blood sampling at the end of infusion, and at 1, 2, 4, 6, 8, 10, 12, and 16 hours after the end of infusion

Day 2, Day 3, and Day 4

Post study drug administration

- Physical examination, including vital signs
- Blood sampling and urine collection for safety lab tests
- PK blood sampling at 24, 36, 48, and 72 hours after the end of infusion
- Recording of AEs (until visit completion) and change in concomitant medications

Visit 2 (Day 8 + Haematology lab test at Day 11)

- Physical examination, including vital signs
- ECOG PS evaluation
- Blood sampling and urine collection for safety lab tests
- Blood sampling for PK only for dose levels ≥ 0.80 mg/kg
- Recording of adverse events and change in concomitant medications

On Day 11, blood sampling for haematology lab test shall be repeated

Visit 3 (Day 15 + Haematology lab test at Day 18)

- Physical examination, including vital signs
- ECOG PS evaluation
- Blood sampling and urine collection for safety lab tests
- Blood sampling for PK only for dose levels ≥ 0.80 mg/kg
- Recording of adverse events and change in concomitant medications

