8.5.4.2 Physical Examinations and Vital signs

A complete physical examination will be performed at Screening, at each day of Visit 1, at Visit 2, at Visit 3 and at the End of Study Visit, which will include a general appearance observation and a complete exam of the following body systems/areas: Head, Eyes, Ears, Nose and Throat (HEENT)/Neck, Lymph Nodes, Thyroid, Abdomen, Skin, Cardiovascular, Respiratory, Gastrointestinal, Neurological, and Musculoskeletal/Extremities.

Vital signs will be recorded throughout the study at Screening, at each day of Visit 1, at Visit 2, at Visit 3 and at the End of Study Visit. At Visit 1, vital signs should be measured prior to study drug administration and every 15 minutes at Cycle 1 and every 30 minutes starting from Cycle 2 during the first hour of study drug administration and then at every hour until the end of the infusion. In case of temporary infusion interruption, vital signs should be collected every 15 minutes until the first hour post-infusion re-start and then every hour until the end of infusion (or until 1-hour after the permanent infusion interruption).

The following parameters will be measured:

- Heart rate (HR; beats / min)
- Blood pressure (BP; systolic and diastolic, mmHg)
- Breathing rate (BR; breaths / min)
- Body temperature (T; °C).

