| Creatinine Uric acid | Anti-HIV Antibodies Anti-HBcAg Antibodies Anti-HBsAg Antibodies HBV-DNA HCV-RNA | Haemoglobin Haematocrit | INR Prothrombin time and/or prothrombin activity Partial thromboplastin time | pH Density |
| Potassium | | RBC count | | Nitrite |
| Phosphorus | | Platelet count MCV WBC count and differential (absolute and %): | | Protein |
| Calcium | | Neutrophil Lymphocyte Eosinophil | | Glucose |
| BUN/Urea Albumin Alkaline phosphatase Glucose Total proteins Total bilirubin and Direct bilirubin ALT and AST LDH GGT Amylase Troponin I or T Sodium Chloride β-HCG (if applicable) | | Basophil Monocytes | | Ketones RBC WBC Epithelial cells Casts Bacteria Yeast Crystals |

8.5.4.6 12-Lead ECG

Twelve-lead ECGs will be performed locally, using standard equipment available at the study sites, during the Screening Period, prior to study drug administration, and 30 minutes after the end of study drug administration at Visit 1 of each cycle and at End of Study Visit.

A standard 12-lead ECG will be performed at rest in the supine position. All ECG print-outs should be identified with patient number, year of birth, and gender, as well as with the date and time of recording. All print-outs should be assessed, dated and signed by the Investigator and stored in the patient's record.

In addition, ECG will be monitored during and up to 30 minutes after each study treatment infusion and any observed abnormalities will be duly recorded.

NOTE:

If ECG monitoring equipment is not available, at Cycle 1 heart rate should be monitored up to 30 minutes after the end of infusion and 12-lead ECG recorded at 30, 60 and 120 minutes during the IV infusion with final 12-lead ECG record at 30 minutes after the end of infusion;

starting from Cycle 2, heart rate should be monitored up to 30 minutes after the end of infusion with final 12-lead ECG record at 30 minutes after the end of infusion.

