e = Vital signs to be collected prior to study drug administration, every 15 minutes at Cycle 1 and every 30 minutes starting from Cycle 2 during the first hour of study drug administration and then at every hour until the end of infusion. In case of temporary infusion interruption, vital signs should be collected every 15 minutes until the first hour post-infusion re-start and then every hour until the end of infusion (or until 1-hour after the permanent infusion interruption).

f = 12-lead ECG record to be performed prior to study drug administration and 30 minutes after the end of the infusion; ECG will be also monitored during IV infusion up to 30 minutes after the end of infusion. If ECG monitoring equipment is not available, at Cycle 1 heart rate should be monitored up to 30 minutes after the end of infusion and 12-lead ECG recorded at 30, 60 and 120 minutes during the IV infusion with final 12-lead ECG record at 30 minutes after the end of infusion; starting from Cycle 2, heart rate should be monitored up to 30 minutes after the end of infusion with final 12-lead ECG record at 30 minutes after the end of infusion.

g = See “Blood Samples Flow Chart and PK Blood Samples Flow Chart” (Section 2.3 and Section 2.4) that includes blood sample collection for safety laboratory tests, β -HCG pregnancy test, Anti-HIV Antibodies, Anti-HBcAg antibodies, Anti-HBsAg antibodies, HBV-DNA, HCV-RNA tests, immunogenicity assessment, free CD205 assessment, flow Cytometry for CD205 expression and DNA sequence of CD205 assessment.

h = TLS Risk Assessment according to Investigator’s TLS manual, will be performed ONLY prior to study drug administration at Visit 1 (Day 1) of Cycle 1 (see [Appendix II](#)).

i = TLS prophylaxis should be given every cycle, if applicable (see [Appendix II](#)).

j = Mandatory premedication with an antihistaminic and an antipyretic (as per local practice) and dexamethasone 20 mg will be administered 30 to 60 minutes prior to study drug administration. Starting from Cycle 3, the dose of dexamethasone can be adjusted upon Investigator’s judgement.

k = After the End of Study Visit, all patients evaluable for efficacy will be followed for survival status according to local practice (a visit or a telephone call) every 12 weeks up to a period of 12 months after first treatment administration to the last patient.

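### The SAP sets baseline by calendar date with no pre-dose condition, so Day 1 blood pressure, heart rate and ECG judgment recorded after dosing began can become the reference for change from baseline

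*SAP*

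**What the plan says.** The SAP gives one general baseline rule (6.1.1.2, Definition of baseline): the "last available (non-missing) value before or on the date of first administration (Visit 1) for Cycle 1". The protocol (9.3.1) plans differences and shift tables to baseline but does not define the term. No other visible section of either document adds a pre-dose condition. The SAP's list of tables and figures (8.1.1.3) is only a heading in the available text.

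The rule feeds two safety summaries in SAP 6.1.1.2:

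- Vital signs and weight: "changes from baseline will be summarised for all scheduled post baseline visits".
- ECG judgment: "Similarly, changes from baseline for each post baseline visit will be summarised".

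Both documents schedule these measurements on either side of the start of the first infusion:

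- Vital signs, SAP flow-chart note e: "Vital signs to be collected prior to study drug administration, every 15 minutes at Cycle 1". Protocol 8.5.1 has the same schedule: "Vital signs every 15 minutes during the first hour of study drug administration and then at every hour until the end of infusion". Protocol 8.5.4.2 gives the visit days: "Vital signs will be recorded throughout the study at Screening, at each day of Visit 1, at Visit 2, at Visit 3", plus the End of Study Visit.
- 12-lead ECG, SAP flow-chart note f: "12-lead ECG record to be performed prior to study drug administration and 30 minutes after the end of the infusion". Protocol 8.5.4.6 schedules it at screening, before dosing, and "30 minutes after the end of study drug administration at Visit 1 of each cycle and at End of Study Visit". If monitoring equipment is not available, Cycle 1 adds recordings at 30, 60 and 120 minutes during the infusion.

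**The concern.** A baseline should describe the patient before exposure. The rule works by date and includes the dosing date, so it can select a value taken during or after the first infusion. The reference would then already contain any acute effect of the drug.

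The protocol gives reasons to care about acute effects. Section 6.3 treats infusion reactions as a risk. It also notes QT shortening seen on Day 1 in monkeys and, while doubting its clinical relevance, adds ECG monitoring to 30 minutes after the infusion.

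At stake are the change-from-baseline summaries for blood pressure, heart rate and ECG judgment, and any shift table of ECG judgment under Protocol 9.3.1. A programmer following the SAP would either pick a post-exposure record or, if the records carry no time or label, have to guess.

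**Working it through.** The plan states no figure to reproduce. The check lists the scheduled records and applies the rule to them.

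**Scheduled records on Cycle 1 Day 1, 3-hour infusion** (Protocol 8.5.1, 8.5.4.2, 8.5.4.6; SAP flow-chart notes e and f)

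| Variable | Pre-dose | After start of infusion | Total | Last on that date |
|---|---|---|---|---|
| Blood pressure, heart rate | 1 | 4 (15, 30, 45, 60 min) + 2 (2 h, 3 h) = 6 | 7 | end of infusion |
| 12-lead ECG, monitoring available | 1 | 1 (30 min after the end) | 2 | post-infusion |
| 12-lead ECG, no monitoring equipment | 1 | 3 (30, 60, 120 min) + 1 = 4 | 5 | post-infusion |
| Safety laboratory tests, weight | 1 | 0 | 1 | pre-dose |

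With separately stored, ordered records, the literal rule takes the 7th vital-sign set and the post-infusion ECG. Scheduled laboratory data and weight keep a pre-dose baseline.

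**Effect on later changes.** Let P be the pre-dose value, E the record selected on Day 1 and V a later visit.

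- Change from a pre-dose baseline: V − P.
- Change under the literal rule: V − E = (V − P) − (E − P).

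Every later change is offset by the same E − P. The offset is zero if the Day 1 change is zero. With assumed systolic values P = 130 and E = 115 (E − P = −15):

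| V | V − P | V − E | Reading |
|---|---|---|---|
| 120 | −10 | +5 | reversed |
| 115 | −15 | 0 | masked |
| 140 | +10 | +25 | inflated |

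For ECG judgment, code Normal 0, abnormal not clinically significant 1, abnormal clinically significant 2. Take P = 0 with E and V both abnormal. The four (E, V) patterns are (1,1), (1,2), (2,1) and (2,2). All four are worse than P. Against E they read no change, worse, improved and no change. This counts patterns, not patients.

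**Which visits carry the offset.** Protocol 8.5.1 defines Cycle 1 Visit 1 as Days 1 to 4, with Visits 2 and 3 on Days 8 and 15. The SAP summarises change by post-baseline visit.

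- Vital signs: Visits 2 and 3 in Cycle 1, also Days 2 to 4 if the table is by day, then Cycle 2 onward and the End of Study Visit.
- ECG: Cycle 2 onward and the End of Study Visit. No 12-lead ECG is scheduled on Days 2 to 4, 8 or 15.

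**A second, independent gap for ECG.** The 30-minute post-infusion ECG belongs to Visit 1, the visit the SAP names for baseline. When monitoring equipment is available it is the only scheduled post-dose 12-lead ECG in Cycle 1, unless an End of Study Visit falls in that cycle. With a pre-dose baseline, Visit 1 may still not count as a post-baseline visit, so this ECG may remain outside the change table.

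**The case against.** The strongest reply is that pre-dose was obviously meant. Both documents separate assessments before dosing from later ones. The SAP dates treatment-emergent events from after first drug intake, and it ties baseline imaging to the period before treatment starts. That intent is probable. But the SAP states the condition in those places and omits it from the general rule, so the wording still needs correction.

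The second reply is that the effect depends on the eCRF layout, which the documents do not show. The SAP mentions only the ECG judgment collected on the eCRF, and nothing says that vital-sign times are entered. This stands: the gap in wording is certain, but selection of a post-exposure record is conditional.

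The third reply is that the safety endpoint for vital signs and ECG is the frequency of clinically significant abnormalities (Protocol 8.5.5.6, SAP 5.1.1.6), which uses no baseline. This also stands and limits the severity.

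Three stronger readings are tempting but not supported:

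- A reader might infer that a pre-dose baseline alone would bring one Cycle 1 post-dose ECG (four without monitoring equipment) into the change table. Those are counts of records. The SAP tabulates by post-baseline visit, and these ECGs sit in Visit 1.
- A reader might infer that all five later Cycle 1 vital-sign days (2, 3, 4, 8, 15) are necessarily affected. Days 2 to 4 belong to Visit 1, so that needs a by-day table.
- A reader might infer that no post-dose Cycle 1 ECG can ever follow the literal baseline. A patient who stops in Cycle 1 has an End of Study ECG, and an unscheduled ECG is also possible.

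**Conclusion.** The baseline rule is wrong as written, with low severity. Read literally, it allows a record taken during or after the first infusion to serve as baseline for blood pressure, heart rate and ECG judgment. That result assumes separate timed or ordered Day 1 records in the eCRF, a non-missing end-of-infusion or post-infusion value, and an infusion and ECG completed on the dosing date. Without times or labels, the baseline record is indeterminate.

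The size of the distortion is each patient's own Day 1 change, which the documents do not allow one to estimate. The worked values show direction only.

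The by-visit ECG summary is a separate gap that would survive correction of the baseline rule.

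The effect stops at descriptive change summaries. A reader might infer that the safety conclusions are compromised, but the documents do not support that. The frequency of clinically significant abnormalities, adverse events, DLT and MTD, scheduled laboratory data, weight, raw by-visit summaries and vital-sign listings do not depend on the affected baseline.

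**What to change.** 1. In SAP 6.1.1.2, define baseline as the last non-missing value before the start (date and time) of the first MEN1309 infusion. Where time is not recorded, use the Day 1 record labelled pre-dose, otherwise the screening value.
2. State that Day 1 infusion and post-infusion records are post-baseline. List the 30-minute post-infusion ECG as a separate Cycle 1 Day 1 time point in the change-from-baseline table.

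Both changes are needed, because the first does not by itself settle where the post-infusion ECG is reported. The cost is SAP wording and minor programming, with no new data collection. ECG print-outs already carry date and time (Protocol 8.5.4.6). For vital signs the pre-dose label is the fallback if times were not entered.
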